## 6.5. Unscheduled Assessments

The determination of baselines and values at the end of treatment for both efficacy and safety variables will be based on available assessments of scheduled and unscheduled visits. For by visit summaries, unscheduled visit will be mapped to a visit using the visit windows described in Section 6.4 and then included in the by-visit summaries.

## 7. TIMING OF STATISTICAL ANALYSES

The analyses will be performed based on two different database locks:

- **Week 36 Analysis:** takes place when the last patient completes the last safety follow-up visit and includes all patient data collected up through the week 36 visit. The efficacy and safety analyses will be conducted at this time.
- **Week 64 analysis:** takes place when the patient data collected up to the time the last patient completes assessments at week 64 phone call. The only additional analysis to be conducted at this time is the analysis of incidence of JRs at the telephone survey approximately 52 weeks after the last dose of study drug and updating of outputs with any data change from the Week 36 Analysis.

**8. INTERIM ANALYSES**

No interim efficacy analysis is planned.

## **9. SOFTWARE**

All clinical data analyses will be done using SAS Version 9.4 and above.

## **11. APPENDIX**

### **11.1. Schedule of Events and Visits**

Study assessments and procedures are presented by study period and visit in [Table 2](#).

**Table 2: Schedule of Events**

	Screening/ Pre-rand		Treatment Period								Follow-up Period						
Study Week	Screen	Pre-rand	Base-line	Wk 1	Wk 2	Wk 4	Wk 8	Wk 12	EOT Wk 16	ET  / JR Pre-op	Wk 20	Wk 24	Wk 28	Wk 32	Wk 36	ET  / JR Pre-op	EOS Wk 64
Study Visit/Phone	Visit 1	Visit 2	Visit 3	Phone 1	Visit 4	Visit 5	Visit 6	Visit 7	Visit 8		Visit 9	Phone 2	Phone 3	Phone 4	Visit 10		Phone 5 
Study Day (visit window)	Up to 30 days	7 to 10 days	1	8 (±1)	15 (±3)	29 (±7)	57 (±7)	85 (±7)	113 (±7)		141 (±7)	169 (±7)	197 (±7)	225 (±7)	253 (±7)		449 (±7)
Screening/Baseline:																	
Inclusion/Exclusion	X	X	X														
Main study informed consent	X																
	X																
Medical history	X																
Medication history	X																
Demographics 	X																
Lumbar spine MRI 	X																
LBPI NRS/eDiary training 		X	X														
BDI-II	X																
Randomization			X														
Patient-Completed Assessments/Efficacy:																	
Patient education brochures 	X	X	X		X	X	X	X									
LBPI NRS 	X	X	X		X	X	X	X	X	X	X						
RMDQ			X		X	X	X	X	X	X							
PGA LBP	X		X		X	X	X	X	X	X							
PHQ-8			X				X		X	X							
WOMAC pain subscale score, both knees and both hips			X						X	X							
Peripheral or central pain assessment			X														
PainDETECT Questionnaire			X														
BPI-sf			X		X	X	X	X	X	X							
MOS Sleep-R			X			X	X	X	X	X							

	Screening/ Pre-rand		Treatment Period								Follow-up Period						
Study Week	Screen	Pre-rand	Base-line	Wk 1	Wk 2	Wk 4	Wk 8	Wk 12	EOT Wk 16	ET  / JR Pre-op	Wk 20	Wk 24	Wk 28	Wk 32	Wk 36	ET  / JR Pre-op	EOS Wk 64
Study Visit/Phone	Visit 1	Visit 2	Visit 3	Phone 1	Visit 4	Visit 5	Visit 6	Visit 7	Visit 8		Visit 9	Phone 2	Phone 3	Phone 4	Visit 10		Phone 5 
Study Day (visit window)	Up to 30 days	7 to 10 days	1	8 (±1)	15 (±3)	29 (±7)	57 (±7)	85 (±7)	113 (±7)		141 (±7)	169 (±7)	197 (±7)	225 (±7)	253 (±7)		449 (±7)
SF-36			X			X	X	X	X	X							
EQ-5D-5L			X			X	X	X	X	X							
WPAI-LBP			X			X	X	X	X	X							
HCRU	X					X			X	X							
TSQM	X					X			X	X							
Treatment:																	
SC study drug injection 			X			X	X	X									
Study drug accountability			X			X	X	X									
Dispense to home paracetamol/acetaminophen		X	X		X	X	X	X									
Paracetamol/acetaminophen accountability			X		X	X	X	X	X	X							
eDiary compliance 			X		X	X	X	X									
Concomitant therapies	X	X	X	X	X	X	X	X	X	X	X	X	X	X	X	X	X
Safety:																	
Weight	X								X	X					X	X	
Vital signs	X	X	X		X	X	X	X	X	X	X				X	X	
Orthostatic blood pressure and heart rate assessment 	X	X	X		X	X	X	X	X	X	X				X	X	
Electrocardiogram	X								X	X							
Physical examination	X								X	X					X	X	
Neurologic examination	X Full		X Brief		X Brief	X Brief	X Brief	X Brief	X Full	X Full	X Brief				X Full	X Full	

	Screening/ Pre-rand		Treatment Period								Follow-up Period						
Study Week	Screen	Pre-rand	Base-line	Wk 1	Wk 2	Wk 4	Wk 8	Wk 12	EOT Wk 16	ET  / JR Pre-op	Wk 20	Wk 24	Wk 28	Wk 32	Wk 36	ET  / JR Pre-op	EOS Wk 64
Study Visit/Phone	Visit 1	Visit 2	Visit 3	Phone 1	Visit 4	Visit 5	Visit 6	Visit 7	Visit 8		Visit 9	Phone 2	Phone 3	Phone 4	Visit 10		Phone 5 
Study Day (visit window)	Up to 30 days	7 to 10 days	1	8 (±1)	15 (±3)	29 (±7)	57 (±7)	85 (±7)	113 (±7)		141 (±7)	169 (±7)	197 (±7)	225 (±7)	253 (±7)		449 (±7)
Survey of autonomic symptoms	X		X		X	X	X	X	X	X	X				X	X	
Joint pain questionnaire	X		X		X	X	X	X	X	X	X				X	X	
Event-triggered imaging 				X	X	X	X	X	X	X	X				X	X	
Adverse events	----->																
SC injection site evaluation			X			X	X	X									
Bilateral X-rays (knee, hip, shoulder)	X 								X 	X 					X 	X 	
MRI (any knee with K-L ≥3 and any hip with K-L ≥2 at screening) 	X																
Pre-op questionnaire (JR) 										X						X	
EOS phone contact 																	X
MRI affected joint(s) - AA patients only 																	X
Laboratory Testing:																	
Hematology 	X					X	X	X	X	X					X	X	
Blood chemistry 	X					X	X	X	X	X					X	X	
ESR	X																
HbA1c 	X																
Urinalysis and urine electrolytes 	X								X	X					X	X	
FSH and estradiol 	X																

	Screening/ Pre-rand		Treatment Period								Follow-up Period						
Study Week	Screen	Pre-rand	Base-line	Wk 1	Wk 2	Wk 4	Wk 8	Wk 12	EOT Wk 16	ET  /JR Pre-op	Wk 20	Wk 24	Wk 28	Wk 32	Wk 36	ET  /JR Pre-op	EOS Wk 64
Study Visit/Phone	Visit 1	Visit 2	Visit 3	Phone 1	Visit 4	Visit 5	Visit 6	Visit 7	Visit 8		Visit 9	Phone 2	Phone 3	Phone 4	Visit 10		Phone 5 
Study Day (visit window)	Up to 30 days	7 to 10 days	1	8 (±1)	15 (±3)	29 (±7)	57 (±7)	85 (±7)	113 (±7)		141 (±7)	169 (±7)	197 (±7)	225 (±7)	253 (±7)		449 (±7)
Pregnancy test (for WOCBP) 	X  Serum		X Urine		X Urine	X Urine	X Urine	X Urine	X Urine	X Urine					X Urine	X Urine	
PK, Antibody, and Research Samples:																	
PK sample 			X		X	X	X		X	X					X	X	
ADA samples 			X						X	X					X	X	
			X														
Biomarker serum and biomarker plasma 			X			X		X	X	X					X	X	

AA: Adjudicated arthropathy  
 ADA: Anti-drug antibody  
 BPI-sf: Brief Pain Inventory-Short Form  
 BDI-II: Beck Depression Inventory - II  
 EOS: End of study  
 EOT: End of treatment  
 ET: Early termination  
 EQ-5D-5L: EuroQoL 5 Dimensions 5 Level Questionnaire  
 ESR: Erythrocyte sedimentation rate  
 FSH: Follicle stimulating hormone  
 HbA1c: Glycated hemoglobin  
 HCRU: Healthcare Resource Utilization  
 JR: Joint replacement  
 LBP: Low Back Pain  
 LBPI: Low Back Pain Intensity  
 MOS Sleep-R: Medical Outcomes Study Sleep Scale Revised  
 MRI: Magnetic resonance imaging  
 NRS: Numerical Rating Scale  
 PGA: Patient Global Assessment  
 PHQ-8: Patient Health Questionnaire 8-Item Version  
 PK: Pharmacokinetic  
 Pre-op: Pre-operative  
 Pre-rand: Pre-randomization  
 RMDQ: Roland Morris Disability Questionnaire  
 SC: Subcutaneous  
 SF-36: 36-item Short Form Survey  
 TSQM: Treatment Satisfaction Questionnaire for Medication  
 Wk: Week  
 WOCBP: Women of childbearing potential  
 WOMAC: Western Ontario and McMaster Osteoarthritis Index  
 WPAI-LBP: Work Productivity and Activity Impairment-Low Back Pain

**Footnotes for the Schedule of Events Table:**

1. Patients who discontinue study drug before week 16 will be encouraged to follow the visit schedule through the remainder of the study. If a patient chooses to end study participation at or before week 16, he/she will be asked to return to the clinic as soon as possible for an early termination (ET) visit.
2. Patients who discontinue study participation after week 16 will be asked to return to the clinic as soon as possible for an early termination (ET) visit following early termination assessments.
3. [REDACTED]
4. Patients' demographic characteristics will be recorded, including age, height, weight, gender, race, and ethnicity.
5. At the request of the central reader, a lumbar spine anterior-posterior/lateral should be obtained if the MRI of the lumbar spine shows evidence suggestive of a destructive or unstable process. Confirmation from the central reader that there are no exclusionary findings on MRI and X-ray (if requested) must be received before a patient can be randomized.
6. Patients will be trained to use the eDiary after initial patient eligibility has been confirmed during the screening period. Patients will use the eDiary to report their daily NRS LBP score (entered to week 20) and daily use of paracetamol/acetaminophen (entered to week 16). Retraining should occur as needed throughout the conduct of the study.
7. At the screening and pre-randomization visits, study staff will review the "Reporting Your Pain" brochure with the patient to ensure the patient understands how to report pain accurately. At subsequent clinic visits, patients will be asked to review the "Reporting Your Pain" brochure themselves. At the screening and baseline visit, study staff will review with the patient the "Participating in a Research Study: What You Need to Know" brochure. At any time during the conduct of the study, patients may require retraining by study staff.
8. Low back pain intensity NRS score will be recorded by the site at the screening visit and at the pre-randomization visit, and by the patient each day (at approximately 6:00 PM) using the eDiary, starting during the pre-randomization period and to week 20.
9. A review of compliance with daily entry of LBPI NRS and rescue medication use will occur at specified study visits, as well as re-education of patients, if applicable. Patients will record their daily LBPI NRS score in the eDiary up to week 20 and their rescue medication usage up to week 16.
10. Study drug administration will be the last procedure at each dosing visit, and will be done after all laboratory samples have been collected and all study assessments and procedures are performed, including blood draws for drug concentration and ADA.

11. Assessments for orthostatic hypotension may be discontinued following regulatory approval if the safety database does not reveal an imbalance for the fasinumab-treated patients.
12. If the pulse is less than 45 bpm at any visit, an ECG with rhythm strip will be obtained and sent to the central reader to confirm the heart rate and rhythm.
13. Imaging (X-ray and/or MRI) will be performed on any joint following a report of clinically significant worsening or exacerbation of pain in that joint. This imaging will be submitted to the adjudication committee for review.
14. If screening radiographs are inconclusive for potential joint-related findings, an MRI of the affected joint must be performed. Confirmation from the central reader that there are no exclusionary findings on X-ray and MRI must be received before a patient can be randomized. Imaging may be performed during pre-randomization, if needed.
15. After the patient has otherwise met study eligibility criteria assessed during the screening period, an MRI of any knee with screening K-L  $\geq 3$  or hip with screening K-L  $\geq 2$  must be performed. Confirmation from the central reader that there are no exclusionary findings on MRI must be received before a patient can be randomized.
16. Imaging assessments (X-rays and MRI) need to be repeated only if it has been  $>30$  days since the joints were last imaged for the modality. If it has been  $\leq 30$  days since imaging assessments were completed, imaging assessments may be completed at the discretion of the investigator.
17. In the event that a patient must undergo JR surgery during the study, the patient will complete the pre-operative visit (early termination assessments, as applicable) and the procedures outlined in the schedule of events for JR follow-up (Table 3). The pre-operative visit should be completed before JR surgery if possible. Pre-operative images will be submitted to the adjudication committee for review.
18. Joint replacement questionnaires are Knee Society Score questionnaire for knee replacements or Harris Hip Score questionnaire for hip replacements.
19. The purpose of this phone contact is to ask the patient if he/she has had or is scheduled (or on a waiting list) to have JR surgery. Pre-operative images will be submitted to the central reader for adjudication, if available.
20. If the AA joint(s) has undergone JR, an X-ray may be substituted for an MRI.
21. Samples will be analyzed by the central laboratory and results will be evaluated by the investigator.
22. The follicle-stimulating hormone (FSH) and estradiol laboratory tests are to be performed only if postmenopausal status has to be assessed for female patients who are  $\leq 59$  years of age.
23. In the event of a positive urine pregnancy test result, the patient must have a serum pregnancy test with a negative result in order to continue study participation. If the serum pregnancy test is positive, the patient must be withdrawn from study drug and should be asked to return to the clinic for all remaining study visits per the visit schedule.

24. PK, ADA, and biomarker samples may also be drawn at any non-specified scheduled visit or any unscheduled visit if a patient experiences a treatment-related safety TEAE. Samples should be collected prior to study drug administration on study drug dosing days.
25. Biomarker samples should be collected after the patients have been fasting overnight or for 8 hours (in the event of an afternoon visit).

**Table 3: Follow up Period for Patients Who Undergo Joint Replacement Surgery**

Follow-up Study Day (Visit Window) 	Post-Operative	Long-Term
	Follow-up Visit 1 4 weeks after joint replacement surgery	Follow-up Visit 2 20 weeks after joint replacement surgery
	Follow-up Day 29 ( $\pm 7$ )	Follow-up Day 140 ( $\pm 7$ )
Treatment:		
Concomitant medications and therapy	X	X
Safety:		
Adverse events	X	X
Vital signs	X	X
Orthostatic blood pressure and heart rate 	X	X
Physical examination with joint exam	X	X
Medical history related to the joint replacement	X	X
Joint pain questionnaire	X	X
Post-operative questionnaire 	X	X
Bilateral X-rays (shoulders, hips, knees) 	X 	X
Event-triggered imaging 	X	X

**Footnotes for Table of Follow-up Period for Patients Who Undergo Joint Replacement Surgery**

1. All available information for patients who undergo JR surgery must be collected, including placement of the prosthesis, healing of the surgical wound, and the results of the histopathologic examination.
2. If it is not possible to obtain orthostatic blood pressure following JR, then blood pressure and pulse should be recorded. Assessments for orthostatic hypotension may be discontinued following regulatory approval if the safety database does not reveal an imbalance for the fasinumab-treated patients.
3. A Knee Society Score questionnaire for knee replacements or Harris Hip Score questionnaire for hip replacements.

4. In the event of more than 1 JR, imaging assessments should be repeated if it has been  $>60$  days since the joints were last imaged. If it has been  $\leq 60$  days since imaging assessments were completed, imaging assessments may be completed at the discretion of the investigator. An MRI may be requested by the imaging vendor after review of the X-rays.
5. Imaging will be done at week 4 if not done pre-operatively.
6. Imaging may be performed on any joint following a report of clinically significant worsening or exacerbation of pain in that joint.

## 11.2. Reference for Criteria for Treatment-Emergent Potentially Clinically Significant Values (PCSV)

The PCSV criteria below should be used as a reference; the actual criteria for each study should be determined and agreed to by the study team prior to database lock as part of SAP and should be based on the study population, indication, and potential effects of study treatment.

**Table 4: Criteria for Treatment-Emergent Potentially Clinically Significant Values (PCSV)**

Parameter	Treatment Emergent PCSV	Comments
Clinical Chemistry		
ALT*	
>3 and <math>\leq</math> 5 ULN and baseline <math>\leq</math> 3 ULN*
 
>5 and <math>\leq</math> 10 ULN and baseline <math>\leq</math> 5 ULN
 
>10 and <math>\leq</math> 20 ULN and baseline <math>\leq</math> 10 ULN
 
>20 ULN and baseline <math>\leq</math> 20 ULN
	
Enzyme activity must be expressed in ULN, not in IU/L.
 
FDA DILI Guidance July 2009.
 
Each category is calculated independently.
 
* At least one level is required; multiple levels are optional for phase 2/3 studies. If it is desirable to get the distribution across the different PCSV levels, additional shift table on <math>\leq</math>3, >3 to <math>\leq</math>5, >5 to <math>\leq</math>10, >10 to <math>\leq</math>20, and >20 category for baseline vs. post baseline may be provided

AST*	
>3 and <math>\leq</math> 5 ULN and baseline <math>\leq</math> 3 ULN*
 
>5 and <math>\leq</math> 10 ULN and baseline <math>\leq</math> 5 ULN
 
>10 and <math>\leq</math> 20 ULN and baseline <math>\leq</math> 10 ULN
 
>20 ULN and baseline <math>\leq</math> 20 ULN
	
Enzyme activity must be expressed in ULN, not in IU/L.
 
FDA DILI Guidance July 2009.
 
Each category is calculated independently.
 
* At least one level is required; multiple levels are optional for phase 2/3 studies. If it is desirable to get the distribution across the different PCSV levels, additional shift table on <math>\leq</math>3, >3 to <math>\leq</math>5, >5 to <math>\leq</math>10, >10 to <math>\leq</math>20, and >20 category for baseline vs. post baseline may be provided

Alkaline Phosphatase	>1.5 ULN and baseline $\leq$ 1.5 ULN	
Enzyme activity must be expressed in ULN, not in IU/L.
 
FDA DILI Guidance July 2009.

Parameter	Treatment Emergent PCSV	Comments
Total Bilirubin*	>1.5 and ≤ 2 ULN and baseline ≤ 1.5 ULN* >2 ULN and baseline ≤ 2.0 ULN	Must be expressed in ULN, not in μmol/L or mg/L. Categories are cumulative.  FDA DILI Guidance July 2009.  * At least one level is required; multiple levels are optional for phase 2/3 studies. If it is desirable to get the distribution of significant level, additional shift table on ≤1.5, >1.5 to ≤2.0 and > 2.0 category for baseline vs. post baseline may be provided
Conjugated Bilirubin	(Direct Bilirubin >35% Total Bilirubin and Total Bilirubin >1.5 ULN) and (Direct Bilirubin ≤35% Total Bilirubin or Total Bilirubin ≤1.5 ULN) at baseline	Conjugated bilirubin dosed on a case-by-case basis.
ALT/AST and Total Bilirubin	(ALT >3 ULN and TBILI>2 ULN) and baseline (ALT ≤3 ULN or TBILI ≤2 ULN)  (AST >3 ULN and TBILI>2 ULN) and baseline (AST ≤3 ULN or TBILI ≤2 ULN)  (ALT >3 ULN and TBILI>1.5 ULN) and baseline (ALT ≤3 ULN or TBILI ≤1.5 ULN)  (AST >3 ULN and TBILI>1.5 ULN) and baseline (AST ≤3 ULN or TBILI ≤1.5 ULN)	FDA DILI Guidance July 2009.
ALT/AST and Total Bilirubin and ALP	(ALT >3 ULN and TBILI>2 ULN and ALP < 2 ULN) and baseline (ALT ≤3 ULN or TBILI ≤2 ULN or ALP ≥2 ULN)  (AST>3 ULN and TBILI>2 ULN and ALP < 2 ULN) and baseline (AST ≤3 ULN or TBILI ≤2 ULN or ALP ≥2 ULN)	FDA DILI Guidance July 2009.

Parameter	Treatment Emergent PCSV	Comments
CPK*	>3 and $\leq$ 10 ULN and baseline $\leq$ 3ULN* >10 ULN and baseline $\leq$ 10ULN	FDA Feb 2005. Am J Cardiol April 2006. Categories are cumulative. * At least one level is required; multiple levels are optional for phase 2/3 studies. If it is desirable to get the distribution of significant level, additional shift table on $\leq$ 3, >3 to $\leq$ 10, and > 10 category for baseline vs. post baseline may be provided
Creatinine	$\geq$ 150 $\mu$ mol/L (Adults) and baseline < 150 $\mu$ mol/L $\geq$ 30% change from baseline and <100% change from baseline $\geq$ 100% change from baseline	Benichou C., 1994 3 independent criteria
Uric Acid		Harrison - Principles of internal Medicine 17 th Ed., 2008.
Hyperuricemia	>408 $\mu$ mol/L and $\leq$ 408 $\mu$ mol/L at baseline	Two independent criteria
Hypouricemia	<120 $\mu$ mol/L and $\geq$ 120 $\mu$ mol/L at baseline	
Blood Urea Nitrogen	$\geq$ 17 mmol/L and <17 mmol/L at baseline	Two independent criteria
Chloride		Two independent criteria
Hypochloremia	<80 mmol/L and baseline $\geq$ 80 mmol/L	
Hyperchloremia	>115 mmol/L and baseline $\leq$ 115 mmol/L	
Sodium		Two independent criteria
Hyponatremia	$\leq$ 129 mmol/L and baseline > 129 mmol/L	
Hypernatremia	$\geq$ 160 mmol/L and baseline <160 mmol/L	
Potassium		FDA Feb 2005.
Hypokalaemia	<3 mmol/L and baseline $\geq$ 3 mmol/L	Two independent criteria
Hyperkalaemia	$\geq$ 5.5 mmol/L and baseline <5.5 mmol/L	
Total Cholesterol	$\geq$ 7.74 mmol/L and < 7.74 mmol/L at baseline	Threshold for therapeutic intervention.

Parameter	Treatment Emergent PCSV	Comments
Triglycerides	$\geq 4.6$ mmol/L and $< 4.6$ mmol/L at baseline	Threshold for therapeutic intervention.
Glucose		
Hypoglycaemia	$\leq 3.9$ mmol/L and $< LLN$ ) and $(> 3.9$ mmol/L or $\geq LLN$ ) at baseline	ADA May 2005.
Hyperglycaemia	$\geq 11.1$ mmol/L (unfasted); $\geq 7$ mmol/L (fasted) and $< 11.1$ mmol/L (unfasted); $< 7$ mmol/L (fasted) at baseline	ADA Jan 2008.
HbA1c	$> 8\%$ and $\leq 8\%$ at baseline	
Albumin	$\leq 25$ g/L and $> 25$ g/L at baseline	
hs-CRP	2 ULN or $> 10$ mg/L (if ULN not provided)	FDA Sept. 2005
Hematology		
WBC	$< 3.0$ Giga/L and $\geq 3.0$ Giga/L at baseline (Non-Black); $< 2.0$ Giga/L and $\geq 2.0$ Giga/L at baseline (Black) $\geq 16.0$ Giga/L and $< 16$ Giga/L at baseline	Increase in WBC: not relevant.  To be interpreted only if no differential count available.
Lymphocytes	$> 4.0$ Giga/L and $\leq 4.0$ Giga/L at baseline	
Neutrophils	$< 1.5$ Giga/L and $\geq 1.5$ Giga/L at baseline (Non-Black); $< 1.0$ Giga/L and $\geq 1.0$ Giga/L at baseline (Black)	International Consensus meeting on drug-induced blood cytopenias, 1991. FDA criteria.
Monocytes	$> 0.7$ Giga/L $\leq 0.7$ Giga/L at baseline	
Basophils	$> 0.1$ Giga/L $\leq 0.1$ Giga/L at baseline	
Eosinophils	$(> 0.5$ Giga/L and $> ULN$ ) and $(\leq 0.5$ Giga/L or $\leq ULN$ at baseline)	Harrison - Principles of internal Medicine 17 th Ed., 2008.

Parameter	Treatment Emergent PCSV	Comments
Hemoglobin	$\leq 115$ g/L and $> 115$ g/L at baseline for male; $\leq 95$ g/L and $> 95$ g/L at baseline for Female. $\geq 185$ g/L and $< 185$ g/L at baseline for Male; $\geq 165$ g/L and $< 165$ g/L at baseline for Female Decrease from Baseline $\geq 20$ g/L	
Three criteria are independent.
 
Criteria based upon decrease from baseline are more relevant than based on absolute value. Other categories for decrease from baseline can be used (<math>\geq 30</math> g/L, <math>\geq 40</math> g/L, <math>\geq 50</math> g/L).

Hematocrit	$\leq 0.37$ v/v and $> 0.37$ v/v at baseline for Male; $\leq 0.32$ v/v and $> 0.32$ v/v at baseline for Female $\geq 0.55$ v/v and $< 0.55$ v/v at baseline for Male; $\geq 0.5$ v/v and $< 0.5$ v/v at baseline for Female	Two Criteria are independent
RBC	Female $< 3$ Tera/L and baseline $\geq 3$ Tera/L $\geq 6$ Tera/L and baseline $< 6$ Tera/L Male $< 4$ Tera/L and baseline $\geq 4$ Tera/L $\geq 7$ Tera/L and baseline $< 7$ Tera/L	
Unless specifically required for particular drug development, the analysis is redundant with that of Hb.
 
Otherwise, consider FDA criteria.

Platelets	$< 100$ Giga/L and $\geq 100$ Giga/L at baseline $\geq 700$ Giga/L and $< 700$ Giga/L at baseline	
International Consensus meeting on drug-induced blood cytopenias, 1991.
 
Two independent criteria

Urinalysis		
pH	$\leq 4.6$ and $> 4.6$ at baseline $\geq 8$ and $< 8$ at baseline	Two independent criteria
Vital signs		
HR	$\leq 50$ bpm and decrease from baseline $\geq 20$ bpm $\geq 120$ bpm and increase from baseline $\geq 20$ bpm	To be applied for all positions (including missing) except STANDING.

Parameter	Treatment Emergent PCSV	Comments
SBP	$\leq 95$ mmHg and decrease from baseline $\geq 20$ mmHg  $\geq 160$ mmHg and increase from baseline $\geq 20$ mmHg	To be applied for all positions (including missing) except STANDING.
DBP	$\leq 45$ mmHg and decrease from baseline $\geq 10$ mmHg  $\geq 110$ mmHg and increase from baseline $\geq 10$ mmHg	To be applied for all positions (including missing) except STANDING.
Orthostatic Hypotension	Su SBP < 160 mmHg - SBP St – Su $\leq - 20$ mmHg DBP St – Su $\leq - 10$ mmHg Su SBP $\geq 160$ mmHg - SBP St – Su $\leq - 30$ mmHg DBP St – Su $\leq - 15$ mmHg	
Weight	$\geq 5\%$ increase from baseline  $\geq 5\%$ decrease from baseline	FDA Feb 2007.
ECG		Ref.: CPMP 1997 guideline. ICH E14 2005
HR	$\leq 50$ bpm and decrease from baseline $\geq 20$ bpm  $\geq 120$ bpm and increase from baseline $\geq 20$ bpm	
PR	$\geq 220$ ms and increase from baseline $\geq 20$ ms	
QRS	$\geq 120$ ms & < 120 ms at baseline	

Parameter	Treatment Emergent PCSV	Comments
QTc	Absolute values (ms)	To be applied to any kind of QT correction formula.
	>450 ms and baseline <=450 ms	
	>480 ms and baseline <=480 ms	
	>500 ms and <= 500 ms at baseline	$\Delta$ QTc>60 ms are the PCSA to be identified in individual subjects/patients' listings.
	Increase from baseline	
	Increase from baseline 30-60 ms	
Increase from baseline >60 ms		

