#### 4.5.6. Orthostatic Hypotension

A patient will be determined to have orthostatic hypotension if any of the following criteria are met:

- If the supine blood pressure is <160 mmHg systolic, a decrease in either the 1 or 3-minute standing systolic blood pressure of  $\geq 20$  mmHg or a decrease in the standing diastolic blood pressure of  $\geq 10$  mmHg from the supine systolic or diastolic blood pressure

OR

- If the supine blood pressure is  $\geq 160$  mmHg systolic, a decrease in either the 1 or 3-minute standing systolic blood pressure of  $\geq 30$  mmHg or a decrease in the standing diastolic blood pressure of  $\geq 15$  mmHg from the supine systolic or diastolic blood pressure

OR

- An increase in either the 1 or 3-minute standing heart rate of  $\geq 30$  bpm from the supine heart rate

OR

- The patient is unable to stand for either one of the standing blood pressure measurements due to dizziness or lightheadedness

Confirmed orthostatic hypotension is defined as initial assessment meeting the above orthostatic hypotension criteria confirmed by subsequent repeated assessments per protocol or if initial assessment met the above orthostatic hypotension criteria yet repeated assessments were not performed.

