## **5.9. Analysis of Safety Data**

The analysis of safety and tolerability will be performed on the SAF, as defined in Section 3.2.

The safety analysis will be based on the reported AEs and other safety information (clinical laboratory evaluations, vital signs, 12-lead ECG, Physical Examination, etc.).

Treatment-Emergent Potential Clinically Significant Values (PCSV) in laboratory variables, vital signs and ECG are defined in Appendix 11.2.

**Period of observation:** The observation period will be divided into three segments: pre-treatment, on-treatment and post-treatment.

- The pre-treatment period is defined as the time between when the patients give informed consent and the start of study drug.
- The on-treatment period is defined as the time from first dose of study drug up to 28 days after the last dose of study drug.
- The post-treatment period is defined as the time starting 29 days after last dose of study drug (after the on-treatment period) to up to 24 weeks post the last dose of study drug (up to week 36).

Day 1 is the first day of study drug, Day -1 is the day before Day 1, and there is no Day 0.

The time interval to detect any on-treatment event or abnormality is between the first dose of double-blind study drug injection and the end of treatment plus 28 days. Data collected outside this interval will be excluded from the on-treatment estimation of descriptive statistics and identification of abnormalities for laboratory evaluations, ECGs and vital signs. All post-baseline data during the interval will be used in the PCSV analysis including scheduled and unscheduled assessments.

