### **5.9.5. Analysis of Vital Signs**

Vital signs (temperature, pulse, blood pressure, orthostatic blood pressure/heart rate, and respiration rate) will be summarized by baseline and change from baseline to each scheduled assessment time with descriptive statistics by treatment group and combined fasinumab for the SAF.

PCSV summary including orthostatic hypotension will be summarized.

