#### ***Missing laboratory, ECG, vital sign, physical exam, neurological exam***

No imputations for missing laboratory data, ECG data, vital sign data, physical examination, or neurological examination data will be made.

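### The orthostatic hypotension row in SAP Table 4 carries two of the four criteria in SAP 4.5.6, so the PCSV summary undercounts against the study's own definition

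*SAP*

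**What the plan says.** The definition is in SAP 4.5.6: "A patient will be determined to have orthostatic hypotension if any of the following criteria are met". Four criteria follow, joined by OR. The first two are standing blood-pressure drops, with thresholds that depend on whether supine systolic pressure is below 160 mmHg or not. The third is "An increase in either the 1 or 3-minute standing heart rate of" 30 bpm or more above supine. The fourth reads "The patient is unable to stand for either one of the standing blood pressure measurements due to dizziness or lightheadedness". Protocol 8.2.3.8 has the same four. SAP 4.5.6 then adds a confirmed category: an initial positive assessment that is borne out by the repeats, or for which no repeats were done.

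The analysis is in SAP 5.9.5: "PCSV summary including orthostatic hypotension will be summarized". For what counts as a PCSV, SAP 5.9 says "Treatment-Emergent Potential Clinically Significant Values (PCSV) in laboratory variables, vital signs and ECG are defined in Appendix 11.2", and SAP 4.5.5 gives the same reference for vital signs, listing orthostatic pressure and pulse among them. In Appendix 11.2 the orthostatic hypotension row of Table 4 starts "Su SBP < 160 mmHg" and gives the two blood-pressure blocks. It has no heart-rate condition, no condition for inability to stand and no confirmation rule, and its comment cell is empty.

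**The concern.** The SAP defines one term in two ways, and its cross-references lead the reported count to the narrower one. A programmer who follows 5.9.5 to 5.9 to Appendix 11.2 never reaches 4.5.6. Patients whom the site determined to have orthostatic hypotension under the protocol could then be missing from the vital-sign summary that carries that name.

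This matters because orthostatic assessment is one of the tools that Protocol 9.6.1.2 lists for monitoring sympathetic nervous system (SNS) dysfunction, which is a safety endpoint and an adverse event of special interest. With dosing stopped, SAP 1.1 gives continued safety monitoring as the purpose of keeping patients in follow-up. A vital-sign table that does not reconcile with the site determinations would need explaining in the study report.

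**Working it through.** The plan states no figure for this point, so there is nothing to reproduce. The check compares the two rules.

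**Criteria side by side**

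| Criterion | SAP 4.5.6 and Protocol 8.2.3.8 | SAP Table 4 row |
|---|---|---|
| Supine SBP below 160: SBP drop of 20 or DBP drop of 10 mmHg | yes | yes |
| Supine SBP 160 or above: SBP drop of 30 or DBP drop of 15 mmHg | yes | yes |
| Standing heart rate up 30 bpm or more from supine | yes | absent |
| Unable to stand for either reading | yes | absent |
| Confirmation by repeat assessment | SAP 4.5.6 only, as a separate category | absent |

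Table 4 therefore holds 2 of the 4 qualifying criteria. It also does not say whether its systolic and diastolic lines are joined by AND or OR, or which standing reading is used. The comparison below assumes OR and either reading, as in 4.5.6. An AND reading would make the row narrower still.

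**Both rules applied to six constructed profiles** (values are SBP/DBP/heart rate)

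| Supine | 1 minute | 3 minutes | Arithmetic | 4.5.6 | Table 4 |
|---|---|---|---|---|---|
| 130/80/70 | 105/75/80 | 110/76/80 | 130 − 105 = 25, at least 20 | yes | yes |
| 165/90/70 | 133/85/80 | 140/86/80 | 165 − 133 = 32, at least 30 | yes | yes |
| 130/80/70 | 125/78/105 | 126/78/104 | heart rate 105 − 70 = 35; SBP drop only 5 | yes | no |
| 130/80/70 | unable | unable | no standing value, no difference | yes | not evaluable |
| 130/80/70 | 120/75/85 | unable | SBP drop 10, DBP drop 5, heart rate +15 | yes | no |
| 130/80/70 | 108/75/85 | unable | 130 − 108 = 22, at least 20 | yes | yes |

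Table 4 misses 3 of the 6. The profiles were chosen to exercise each criterion, so 3 of 6 is not an estimate of how often patients would be missed.

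**Whether another PCSV rule recovers the missed patients**

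- Missing standing readings: SAP 6.3 says "No imputations for missing laboratory data, ECG data, vital sign data, physical examination, or neurological examination data will be made", so a patient with no standing reading can never be flagged by a standing-minus-supine rule.
- The heart-rate row of Table 4 excludes standing readings and works on change from baseline, so it does not capture a rise from supine to standing.
- The by-visit orthostatic pressure and heart-rate summaries in 5.9.5 are descriptive statistics of values and changes. They do not count patients who meet a definition.

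**Confirmed category.** SAP 5.9 admits all post-baseline values in the interval to the PCSV analysis, scheduled and unscheduled, and Table 4 asks for no repeat. A single drop that the repeats did not bear out would count in the row but would not be confirmed under 4.5.6. No planned output names the confirmed category.

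**Scale.** SAP 1.1 reports 63 randomized patients. If they split about evenly into 31 and 32 (an assumption; the split and the size of the safety set are not given), one omitted patient moves an arm's percentage by 1/32 = 3.1 to 1/31 = 3.2 points.

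**The case against.** The strongest reply is that Appendix 11.2 presents Table 4 as a reference, with the actual criteria to be agreed by the study team before database lock. The table does look generic: it has cholesterol and triglyceride rows, although the chemistry panel in Protocol 8.2.3.12 lists neither. On this view 4.5.6 is the study-specific definition and 5.9.5 can be read as using it. This has some force, since the team could apply 4.5.6. But the SAP does not say so, 5.9 refers to the appendix without qualification, 5.9.5 does not cite 4.5.6, and the same sentence in 11.2 wants the final criteria settled as part of the SAP, which offers no other PCSV rule for orthostatic hypotension.

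Other objections limit how far the point reaches, and they stand:

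- A reader might infer that these patients disappear from safety reporting. They need not. Protocol 9.6.1.2 has a patient determined to have orthostatic hypotension entered as an adverse event, and SAP 5.9.2 tabulates treatment-emergent events.
- A reader might infer that the SNS dysfunction endpoint is biased. It rests on specialist diagnosis, and no Table 4 count feeds it.
- A reader might infer that every patient who could not stand is missed. The fourth criterion is met if either reading fails, so a patient with one reading that shows a qualifying drop is still flagged, as the last profile shows.
- A reader might infer a plain undercount throughout. That holds against the any-criterion definition. Against the confirmed category, the missing repeat step can also overcount.
- A reader might take the omitted cases to be the most severe. Neither document ranks the criteria.

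**Conclusion.** Wrong as written, with an effect limited to one descriptive safety table. Followed literally, the PCSV summary omits patients who meet 4.5.6 only through a heart-rate rise or only through inability to stand. It undercounts against the any-criterion definition and need not agree with cases determined under the protocol. It does not measure the confirmed category either.

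The number of patients affected cannot be derived from the documents. No hypothesis test depends on this table, since SAP 5.8 drops testing altogether. The conclusion assumes that Table 4 is applied as 5.9 directs. If the team had already decided to use 4.5.6, the defect would reduce to missing documentation, and the correction would be the same.

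**What to change.** Replace the content of the Table 4 orthostatic hypotension row with a reference: as defined in Section 4.5.6 (any of four criteria). In 5.9.5, state that the number and percentage of patients with any and with confirmed orthostatic hypotension per 4.5.6 will be tabulated by treatment group for the safety set. The cross-reference also settles whether the systolic and diastolic conditions are joined by OR and which standing readings count.

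This changes analysis text only; clinical procedures stay as they are. The cost is one table row, one sentence and minor programming. It assumes that inability to stand through dizziness or lightheadedness is recorded as a field on the CRF, which the documents do not show. If it is not, the SAP should say how such patients will be identified, or state that the table cannot include them. The change should be made before database lock.
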